5.1. Study Population

The study will include eligible vaccinees enrolled in Medicare during the study period who receive an influenza vaccine and meet the inclusion and exclusion criteria below, regardless of AE occurrence. All eligible vaccinees will be used to estimate attributable risks (ARs), whereas a subset population with an observed AE occurrence during the observation period (case population) will be used to estimate IRRs.

Inclusion criteria

- (i) Beneficiaries must be enrolled in Medicare Part A (inpatient insurance) and Part B (outpatient and physician services insurance) FFS plans during the observation period, which extends from vaccination date through the earlier of the AE control period end, or any of the censorship criteria (i.e., disenrollment, subsequent influenza vaccination, study period end, or death). Definitions for the risk, control and observation period can be referenced in Section 5.4.
 - If a follow-up concomitant vaccines analysis is applicable, Part D insurance will also be required during the observation period to ensure comprehensive capture of concomitant vaccinations.
- (ii) Beneficiaries must have received an influenza vaccine during the study period and prior to the vaccination cutoff date (latest date vaccine administration will be eligible for inclusion in the study). Further information on the rationale for this cutoff is provided in Section 5.5.1.
- (iii) Beneficiaries will be required to have continuous enrollment in Medicare Parts A and B FFS from 365 days prior to influenza vaccination through the earlier of the observation period end, or any of the censorship criteria (i.e., disenrollment, subsequent influenza vaccination, or death).

- (iv) For the case population only, each case must have a record of an incident AE diagnosis during the observation period.

Exclusion criteria

- (i) Medicare beneficiaries less than 65 years of age at the time of influenza vaccination.
- (ii) Individuals that do not contribute *any* follow-up time to both risk and control intervals i.e. beneficiaries that meet any of the censorship criteria during the risk interval prior to accumulating time in the control interval will be excluded.
- (iii) Individuals vaccinated with multiple influenza vaccine brands on the same day or multiple influenza vaccinations (same/different brand) within 3 days of each other.
- (iv) People who received a diagnosis of the AE during the AE-specific clean period.

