5.2 Self-Controlled Methods

The SCCS design compares the incidence of AEs during periods of hypothesized excess risk due to the exposure (risk intervals) to the incidence of AEs during all other times (or selected times) during the observation period (control intervals). Only beneficiaries with an incident AE during the observation period (case population) are sampled in the SCCS design, with estimation of incidence occurring within, rather than between, individuals. The SCCS design has a number of assumptions that have to be met in order to ensure unbiased incidence rate estimates, specifically that⁽²⁶⁾:

- (i) Occurrence of an event does not substantially affect subsequent exposures.
- (ii) Occurrence of an event does not affect the observation length.
- (iii) Event rates are constant within risk intervals.
 - a) Events must be independently recurrent or rare.
- (iv) Risk and control intervals are correctly specified.

Certain modifications to the SCCS design will be performed to reduce potential violations to these assumptions. Study analyses will be restricted to the post-vaccination control interval to reduce bias from reverse causation, where early occurrences of an event affect the likelihood of subsequent exposures resulting in accentuated or attenuated effect associations between the exposure and outcome. An adjustment developed by Farrington et al. will also be implemented to adjust for perturbed or curtailed observation time. This will involve conditioning on the age at censoring in cases, and weighting cases by the density of follow-up time from event to censoring.⁽²⁷⁾ The case fatality rate can range from 10-13% for certain AEs such as GBS, encephalitis or encephalomyelitis, and transverse myelitis.⁽²⁸⁻³⁰⁾ As AE-related mortality would violate the assumption that events be independent of the observation length, this adjustment is required to reduce the potential bias from event-dependent observation lengths.

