5.4 Risk and Control Interval

5.4.1 Definition of Observation Period, Risk and Control Intervals

Specifications for AE-specific risk and control intervals are presented in Section 4.3.

Figure 1 presents a hypothetical example of the observation period for a person that experiences a qualifying GBS event following influenza vaccination. The observation period for this person will begin on the vaccination date and extend to 90 days following vaccination, including a 42-day risk interval, and a control interval extending from day 43 to day 90 following vaccination. Risk and control intervals for individuals will vary by AE and based on the presence of any censorship criteria. AE-specific risk and control interval specifications can be referenced in Section 4.3.

Figure 1. Hypothetical Example of Observation Period, Risk and Control Interval for Individual with a Qualifying GBS Event Following Influenza Vaccination

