5.4.1.1 Observation Period

The observation period length will be AE-specific. For each individual, the observation period will start from the day following influenza vaccination (except for anaphylaxis which will begin on the day of vaccination) and extend through the earlier of the end of the AE-specific control interval, study period end, or any of the specified censorship criteria (i.e., disenrollment, subsequent influenza vaccination).

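### Exclusion (ii) drops cases who die before control time begins, so early fatal events leave the descriptive counts and the attributable-risk numerator

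*Protocol*

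**What the plan says.** Exclusion (ii) in Protocol Section 5.1 states that "beneficiaries that meet any of the censorship criteria during the risk interval prior to accumulating time in the control interval will be excluded". Inclusion criterion (i) in the same section ends observation at the control period end or "any of the censorship criteria (i.e., disenrollment, subsequent influenza vaccination, study period end, or death", and inclusion criterion (iii) also names death. The definition of the observation period in Section 5.4.1.1 lists "any of the specified censorship criteria (i.e., disenrollment, subsequent influenza vaccination" and leaves death out.

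Section 5.2 recognises that fatal events are a problem for the design: "The case fatality rate can range from 10-13% for certain AEs such as GBS, encephalitis or encephalomyelitis, and transverse myelitis". Its answer is the Farrington adjustment, which means "weighting cases by the density of follow-up time from event to censoring", and it says that "this adjustment is required to reduce the potential bias from event-dependent observation lengths". Section 5.5.3.1 puts this adjustment into every planned inferential model.

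For Guillain-Barré syndrome the windows are described as "including a 42-day risk interval, and a control interval extending from day 43 to day 90 following vaccination". Table 4 gives the same windows for encephalitis and transverse myelitis, and days 0-1 (risk) and 3-16 (control) for anaphylaxis. Section 5.5.6 defines the AR as model-based excess cases divided by eligible beneficiaries. Section 5.1 makes eligibility subject to exclusion (ii).

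**The concern.** The rule selects on an outcome of the event under study, and it acts on one side only. A case with an event in the control interval has reached control time by definition, so the rule cannot touch it. A case with onset on days 1-42 who dies before day 43 is removed. For anaphylaxis, a case who dies on day 0 or 1 is removed. Day 2 is unclear, because it lies between the two intervals and the explanatory clause of exclusion (ii) speaks only of the risk interval.

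The Farrington weights are meant to handle observation cut short by the event, but they act only on cases that are in the data set. They cannot put an excluded case back into a table of counts or into the AR numerator. In a safety study the events lost are the most severe and the closest to vaccination, and the protocol does not plan to report how many were removed.

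**Working it through.** **Inputs from the protocol.** Case fatality (CFR) 10-13% (Section 5.2); risk days 1-42 and control days 43-90 (Table 4).

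**Assumptions.** Time from event to death is exponential with mean m = 7, 14 or 28 days, because the protocol gives no distribution. Event days are uniform within each interval. The AR denominator is treated as fixed. Excess cases are read from Section 5.5.6 as a × (1 − 1/IRR), where a is the number of risk-interval cases.

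The protocol states no figure for this loss, so there is none to reproduce.

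**Step 1: share of risk-interval cases lost.**

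q = CFR × mean over t = 1..42 of [1 − exp(−(43 − t)/m)]

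For m = 7 the mean term is 0.845, so q = 0.10 × 0.845 = 8.5% or 0.13 × 0.845 = 11.0%. For m = 28 the two values are 4.9% and 6.4%. The range is about 5-11%. The corresponding share of control-interval cases is zero.

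**Step 2: effect on the IRR.** I simulated 1,000,000 cases per scenario. The weight for an event at day t is π·f(b − t) for a death at day b, and 1 − π·F(90 − t) for a case alive at day 90. Here π is the fatality, and f and F are the density and distribution function of time to death. With weights held fixed, the fitted IRR was the same to three decimals with and without the excluded cases. A case with only risk time has conditional likelihood 1 and carries no information on the IRR. The IRR moves only when π and f are estimated from the cases left after the exclusion. At true IRR 1 it is then 0.97-0.99, against 1.00 with weights from all cases.

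**Step 3: effect on the AR at true IRR 1.5.** The share of the true excess that is kept is

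(1 − q) × (1 − 1/IRR_fitted) / (1 − 1/1.5)

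If the fitted IRR is correct, this is 1 − q, so the shortfall equals q. If the weights are fitted after the exclusion, both factors fall. For CFR 13% and m = 7: 0.890 × (1 − 1/1.476) / 0.3333 = 0.861, which is 13.9% too low.

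| CFR | m (days) | q | IRR, weights from all cases | IRR, weights after exclusion | AR shortfall, all-case weights | AR shortfall, post-exclusion weights |
|---|---|---|---|---|---|---|
| 10% | 7 | 8.5% | 1.499 | 1.481 | 8.6% | 10.7% |
| 10% | 14 | 6.9% | 1.498 | 1.464 | 7.2% | 11.5% |
| 10% | 28 | 4.9% | 1.499 | 1.459 | 5.1% | 10.3% |
| 13% | 7 | 11.0% | 1.500 | 1.476 | 11.0% | 13.9% |
| 13% | 14 | 9.0% | 1.499 | 1.453 | 9.1% | 14.8% |
| 13% | 28 | 6.4% | 1.505 | 1.452 | 5.8% | 12.6% |

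No control-interval case was removed in any scenario. Small gaps between q and the all-case shortfall are simulation error in the fitted IRR.

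**Anaphylaxis.** The protocol gives no fatality, so I give no size. The loss follows from the rule itself.

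**The case against.** The strongest reply is that exclusion (ii) mostly formalises what the conditional model already does. A person censored inside the risk interval has no control time and cannot inform the IRR whether kept or dropped. This stands for the IRR, and step 2 confirms it.

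A reader might infer that the exclusion pulls the main IRR down by the full share of lost cases, for example from 1 to 0.89-0.95 (1 − q). The documents do not support that. Such a figure needs an unweighted model that gives every case the full 42 + 48 days. The protocol ends observation at censoring and puts the Farrington adjustment in every inferential model. An unweighted model on observed time is biased downward, but by the same amount with or without the exclusion. That bias comes from curtailed follow-up and is what the adjustment is there to correct.

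It can also be said that the protocol does not state which cases are used to estimate the event-to-censoring density, and that a statistical analysis plan may settle this. That is fair, and it is why the IRR effect is given only as a conditional range. A further point is that the AR is derived from the weighted model and so inherits its correction. This is true of the rate ratio inside the AR. It is not true of the number of cases to which the ratio is applied, and the shortfall of q remains even with the best weights.

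Finally, the time to death is assumed. A longer mean gives a smaller loss, and the loss cannot exceed the case fatality of 10-13%.

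**Conclusion.** The point holds for the descriptive counts and the AR. As written, exclusion (ii) combined with death as a censorship criterion removes fatal risk-interval cases and never control-interval cases. With 10-13% fatality and an assumed mean time to death of 7-28 days, about 5-11% of risk-interval cases for the three neurological events are lost. At a true IRR of 1.5 the AR is about 5-11% too low, rising to 10-15% if the weights are fitted after the exclusion.

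The IRR is a secondary matter. It is unchanged for given weights, and low by about 0-4% only under post-exclusion weight estimation. It would be wrong to conclude that the primary hypothesis test is seriously compromised.

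The omission of death from the list in Section 5.4.1.1 is a separate inconsistency. Programmers following one section or the other could build different cohorts. This should be fixed before analysis, but it does not invalidate the design.

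**What to change.** Limit exclusion (ii) to censoring other than death, that is, disenrollment and repeat influenza vaccination. Keep cases who die after the event in three places: the descriptive counts, the AR numerator, and the estimation of the event-to-censoring density for the Farrington weights. Apply the same rule to all vaccinees so that the AR numerator and denominator match. Report, by event, how many cases died before reaching control time. Make Sections 5.1 and 5.4.1.1 agree on whether death is a censorship criterion, and state how a death on day 2 is treated for anaphylaxis.

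The cost is a change of wording and a small change to the cohort filter, using data already held. The retained cases add no information to the conditional IRR, so precision does not improve. The gain is in complete counts and a correct AR.

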5.2 Self-Controlled Methods

The SCCS design compares the incidence of AEs during periods of hypothesized excess risk due to the exposure (risk intervals) to the incidence of AEs during all other times (or selected times) during the observation period (control intervals). Only beneficiaries with an incident AE during the observation period (case population) are sampled in the SCCS design, with estimation of incidence occurring within, rather than between, individuals. The SCCS design has a number of assumptions that have to be met in order to ensure unbiased incidence rate estimates, specifically that⁽²⁶⁾:

- (i) Occurrence of an event does not substantially affect subsequent exposures.
- (ii) Occurrence of an event does not affect the observation length.
- (iii) Event rates are constant within risk intervals.
 - a) Events must be independently recurrent or rare.
- (iv) Risk and control intervals are correctly specified.

Certain modifications to the SCCS design will be performed to reduce potential violations to these assumptions. Study analyses will be restricted to the post-vaccination control interval to reduce bias from reverse causation, where early occurrences of an event affect the likelihood of subsequent exposures resulting in accentuated or attenuated effect associations between the exposure and outcome. An adjustment developed by Farrington et al. will also be implemented to adjust for perturbed or curtailed observation time. This will involve conditioning on the age at censoring in cases, and weighting cases by the density of follow-up time from event to censoring.⁽²⁷⁾ The case fatality rate can range from 10-13% for certain AEs such as GBS, encephalitis or encephalomyelitis, and transverse myelitis.⁽²⁸⁻³⁰⁾ As AE-related mortality would violate the assumption that events be independent of the observation length, this adjustment is required to reduce the potential bias from event-dependent observation lengths.

5.3 Study Period

The study period will start on August 1, 2022, the effective date for billing codes for influenza vaccinations approved during the 2022-2023 influenza season,⁽²²⁾ and end on June 2, 2023. The study end date was determined based on the approach detailed in Section 5.5.1 and was established to account for claims delay in the data.

[figure not shown]
5.4 Risk and Control Interval

5.4.1 Definition of Observation Period, Risk and Control Intervals

Specifications for AE-specific risk and control intervals are presented in Section 4.3.

Figure 1 presents a hypothetical example of the observation period for a person that experiences a qualifying GBS event following influenza vaccination. The observation period for this person will begin on the vaccination date and extend to 90 days following vaccination, including a 42-day risk interval, and a control interval extending from day 43 to day 90 following vaccination. Risk and control intervals for individuals will vary by AE and based on the presence of any censorship criteria. AE-specific risk and control interval specifications can be referenced in Section 4.3.

Figure 1. Hypothetical Example of Observation Period, Risk and Control Interval for Individual with a Qualifying GBS Event Following Influenza Vaccination

5.4.1.1 Observation Period

The observation period length will be AE-specific. For each individual, the observation period will start from the day following influenza vaccination (except for anaphylaxis which will begin on the day of vaccination) and extend through the earlier of the end of the AE-specific control interval, study period end, or any of the specified censorship criteria (i.e., disenrollment, subsequent influenza vaccination).

5.4.1.2 Risk Interval

The risk interval is similarly AE-specific and is defined as the time during which excess risk is hypothesized following influenza vaccination based on biological plausibility and clinical input. Table 4 in Section 4.3 displays the risk intervals that are used for each AE.

5.4.1.3 Control Interval

The control interval is restricted to the post-vaccination period and is defined as all follow-up time during the observation period following an influenza vaccine that occurs after the risk interval.

5.5 Statistical Analysis

A feasibility analysis will first be conducted as outlined in Section 5.5.1 to determine the study end date. Descriptive and inferential analyses will then be conducted for primary and follow-up analyses (if applicable) as specified in Section 5.5.2-Section 5.5.6.

5.5.1 Feasibility Analysis: Statistical Power and Sample Size

A power analysis will be performed to determine when the analyses can be conducted with sufficient sample size. This will be used to establish the data cut for the analysis, which will inform the study end date. The influenza vaccination uptake distribution in the 2022-2023 influenza season will first be obtained to ensure that the vaccination cutoff date (only vaccines prior to this cutoff will be eligible for inclusion in the study) is selected to capture at least 85% of vaccinations. Then, for each AE, vaccine cutoff date, and influenza vaccine group (reference Table 3), the outcome-specific data cut date will be estimated based on (i) the length of the observation window and (ii) the outcome-specific claims delay distribution with a 90% data completeness requirement. For each AE, vaccination cutoff date and influenza vaccine group, the expected number of events during the observation window will be estimated using the AE-specific historical background rates obtained from 2021. Finally, the minimum detectable IRR will be estimated, defined as the minimum effect size that can be detected in the study based on the expected sample size at 80% power and a two-sided alpha of 0.05. To determine if there is sufficient power to conduct the analysis, for each AE, vaccination cutoff date, and influenza vaccine group, we will identify comparable IRR estimates available in the literature. These will be compared against the minimum detectable IRR estimated in the power analysis, so that the data cut date/study end date used for the analysis can balance the trade-off between being able to detect reasonable differences in incident rates and the timely initiation of analyses.

The 90% completeness threshold was selected to balance the potential bias due to observation of partially accrued post-vaccination control intervals relative to risk intervals and timeliness of the analyses. Assuming that event observation delays are accurately estimated from historical data, a 90% completeness threshold limits the difference in observation of events in risk intervals (at most 100% complete) versus control intervals (at minimum 90% complete). If the true IRR is 1, the bias due to observation delay is $(1/0.9)-1=11\%$. However, in practice, risk and control interval completeness will fall between 100% and 90% and we expect the potential bias due to claims delay to be smaller. The 90% completeness is likely to overestimate the IRR by 10% or less.

5.5.2 Descriptive Analysis

Descriptive analyses will be performed for the primary and follow-up analyses. For each of the case populations, the descriptive analyses will summarize the cases (counts and percentages) and unadjusted outcome rates following influenza vaccination by risk and control intervals. Descriptive statistics will be summarized for influenza vaccines overall and by high-dose and adjuvanted vaccine groups. Statistics will be summarized overall and by the following characteristics.

- (i) Demographics: Age, sex, race/ethnicity, dual eligibility status, region³, urban/rural, area deprivation index (ADI)⁽³¹⁾, nursing home residency status
- (ii) Health status: Influenza diagnosis (defined by the ICD-10-CM code J10.X) in the 30 days prior to influenza vaccination
- (iii) Concomitant vaccines administered on the influenza vaccine administration date (as specified in Section 2)
- (iv) Baseline health characteristics (defined by ICD-10 codes) in the 183 days prior to influenza vaccination:
 - Prior hospitalization
 - Asthma
 - Blood disorders
 - Chronic lung disease
 - Diabetes
 - Heart disease
 - Kidney disorders
 - Liver disorders
 - Neurological or neurodevelopmental conditions
 - Malignant neoplasms
 - Immunocompromised status (as binary covariate)⁴⁽³²⁾
 - Charlson comorbidity index

5.5.3 Primary Inferential Analysis

5.5.3.1 Incidence Rate Ratio (IRR) Estimation

The primary inferential analysis will evaluate the incidence rates of AEs following the influenza vaccines, comparing the rates of AEs in the risk and control intervals using a conditional Poisson regression model, conditioning on the total number of AEs observed for an individual patient in the observation period. This analysis will be restricted to the case population and conducted for each AE for influenza vaccines overall and by high-dose and adjuvanted vaccine groups.

The main primary analysis model will include a Farrington, seasonality and positive predictive value (PPV) adjustment (for AEs with PPVs available based on medical record review). The Farrington adjustment will be used to account for the reduced observation time that can occur from the occurrence of an event.⁽²⁷⁾ A separate analysis will be conducted including Farrington and PPV adjustments only, to evaluate the independent effect of the PPV adjustment excluding the seasonality adjustment. Another separate analysis will be performed including Farrington and seasonality adjustments only to evaluate

³ Covariate will be based on Health and Human Service (HHS) Region as specified on <https://www.hhs.gov/about/agencies/iea/regional-offices/region-1/index.html>

⁴ Beneficiaries' immunocompromised status will be determined based on a CBER-modified algorithm adapted from the Greenberg et al. algorithm, which was developed and validated to identify immunocompromised persons. Details on the algorithm can be found in Appendix 10.21.

the independent effect of the seasonality adjustment. The approach for the seasonality and PPV adjustments are specified in Section 5.5.5.

